7.14 Rescue medication

Subjects will be permitted to take acetaminophen (paracetamol) tablet as needed during the treatment period. Any use of rescue medication will be recorded by the subject in the subject diary (e.g., Date and time). [REDACTED]

Y

Digitized by [contact]

Digitized by [contact]

Digitized by [contact]

[REDACTED]. Rescue medications will not be permitted within 3 days of the assessments during treatment period. Use of rescue medications by subjects during this period for intolerable pain will require rescheduling the visits in such a way that visits happen after at least 3 days of stopping rescue medication and subjects will be required to inform the site about the rescue

medication use. Site staff will telephonically remind to subjects regarding stop usage of rescue medication before the visit and next visit date. The use of rescue medication will be compared between treatment groups.

8 EFFICACY ASSESSMENTS

8.1 Western Ontario and McMaster Universities Osteoarthritis Index (WOMAC) Likert Scale

3.1

Western Ontario and McMaster Universities Osteoarthritis Index is used to assess pain, stiffness, and physical function in subjects with hip and / or knee osteoarthritis (OA).

The WOMAC consists of 24 items divided into 3 subscales¹³:

- Pain (5 items): during walking, using stairs, in bed, sitting or lying, and standing
- Stiffness (2 items): after first waking and later in the day
- Physical Function (17 items): stair use, rising from sitting, standing, bending, walking, getting in / out of a car, shopping, putting on / taking off socks, rising from bed, lying in bed, getting in / out of bath, sitting, getting on / off toilet, heavy household duties, light household duties

Among all the 3 subscales, pain score will be used during the study.

[figure not shown]
Western Ontario and McMaster Universities Osteoarthritis Index (WOMAC) pain score will be recorded at the start and at the end of run-in Period (i.e. immediately prior to randomization on the day of baseline visit); and on Week 2 and Week 4 for target knee after start of treatment.

WOMAC pain score (pain score = 0 to 20), will be determined by the subject's responses to five questions (S1–S5) using a 5-point Likert scale (i.e., 'none'=0; 'mild'=1; 'moderate'=2; 'severe'=3; 'extreme'=4). The questions pertain to the amount of pain the subject is currently experiencing in the target knee [i.e., 'How much pain do you have' when 'Walking on a flat surface' (S1), 'Going up or down stairs' (S2), 'at night while in bed' (S3), 'Sitting or lying' (S4), 'Standing upright' (S5)]. WOMAC pain score will be given to the subject along with the necessary instruction on the each visit.

8.2 Pain on movement (POM) after 100 Meter Walk on a Visual Analog Scale (VAS)

Pain on movement (POM) on a Visual Analog Scale (VAS) will be determined by the subject's responses at the start and at the end of run-in Period (i.e. immediately prior to randomization on the day of baseline visit); and on Week 2 and Week 4 after start of treatment for the both the knees. The subject will be asked to place a mark to the VAS line at the point that represents pain intensity. The VAS score will be determined by measuring in millimetres from the left hand end of the line to the point that the patient marks by site staff. The calibrated ruler will be used to estimate VAS score.¹⁴

VAS scale:

9 SAFETY ASSESSMENTS

9.1 Adverse Events

Safety will be determined by monitoring adverse events (AEs), which will be classified using MedDRA (Medical Dictionary for Regulatory Activities) terminology.

9.2 Medical History

A complete medical history, including a complete review of all current and past diseases and their respective treatments, must be done on screening visit.

9.3 Physical Examination

The investigator or sub-investigator must perform a physical examination on screening, baseline visit, interim visit (on day 14) and end of study visit.

Joint examination of the affected knee will be performed during the screening includes following:

- Recording of affected knee (left/right)
- Receiving any physical therapy at screening
- Subjects with periarticular pain
- Range of motion
 - ⇒ Extension (degree)
 - ⇒ Neutral (degree)
 - ⇒ Flexion (degree)
- Tenderness on pressure (scale: 0 = none, 1=mild, 2=moderate and 3=severe)
 - ⇒ Joint space medially
 - ⇒ Joint space laterally
 - ⇒ Patella medially
 - ⇒ Patella laterally
- Swelling of joint capsule(scale: 0 = none, 1=slight, 2=moderate and 3=severe)
- Joint effusion (Yes/No)

Vital signs (heart rate, respiratory rate, body temperature and blood pressure) will be measured after 5 minutes of rest (sitting) on each visit.

A standard 12-lead ECG will be recorded after 5 minutes of rest in the supine position on screening visit and on end of study visit.

X-ray of target knee will be performed on screening if not performed for more than 1 year prior to baseline.

9.4 Application Site Reaction

Application site reaction will be assessed on each visit after start of run-in period to evaluate the adverse events if any.

9.5 Laboratory Tests

Following laboratory tests will be performed at screening and at the end of the study:

Hematology				
Hemoglobin	Total RBC count	Total WBC count	Platelet count	
Differential Leukocyte count:				
Neutrophils	Lymphocytes	Eosinophils	Monocytes	Basophils
Blood Chemistry				
Alkaline Phosphatase	Serum Creatinine	Random Glucose	SGPT & SGOT	
Serum Bilirubin				

If the gap between screening laboratory assessments (hematology and biochemistry) and baseline visit is more than 14 days, the lab assessments should be repeated at baseline visit

If warranted, other tests or examinations may be performed at the discretion of the Principal Investigator. Approximately 20 ± 5 ml of blood will be withdrawn during screening visit and at the end of study visit to perform above mentioned Clinical Laboratory Tests.

9.6 Pregnancy Test

Serum Pregnancy Test for females of childbearing potential will be performed during screening visit and at the end of study or early termination visit. The urine pregnancy test can be performed if clinically indicated during other visits. If urine pregnancy is found to be positive, serum pregnancy will be done for confirmation. If serum pregnancy test will found positive then patient will be excluded from the study and followed up.

Acceptable forms of contraception include the following:

- Oral Contraceptives or Intrauterine Device in place for at least 3 months prior to the start of the study and remaining in place during the study period, or
- Double Barrier methods containing or used in conjunction with a spermicidal agent, or
- Contraceptive Patches/ Implants, or
- Abstinence: Subjects who will be practicing abstinence will agree to have a documented second acceptable method of birth control if the subject become sexually active during the course of her study participation.

10 SCHEDULE OF ACTIVITIES: (VISIT SCHEDULE)

10.1 Visit 1: Screening Visit (within 28 days prior to randomization)

- **Informed Consent:** Subjects must provide a signed, IEC/IRB approved written informed consent. No study related procedures or activities will be performed until each subject is fully informed and the consent form is signed and dated. All subjects will be given a copy of the signed and dated consent form.
- **Inclusion/Exclusion Criteria Review**
- **Demographic Data** (Height, weight, age, sex, ethnicity etc.)
- **Medical History.** A complete medical history will be recorded. Information regarding the subject's current and past medical conditions will be captured including surgical procedures.
- **Physical Examination (along with baseline joint examination)and Vital Signs**
- **Evaluation of ACR criteria for OA**
- **Laboratory Tests**
- **X-ray of target knee, evaluation as per the Kellgren-Lawrence grading** (See [Appendix III](#))
- **ECG**
- **Serum Pregnancy Test** (for all females of childbearing potential)
- **Assess Adverse Events** (after signing of the ICF)

10.2 Visit 2: Start of Placebo Run-in Period (Day -11 to Day -7)

- **Discontinuation of current osteoarthritis therapy**
- **Vital Signs**
- **Inclusion/Exclusion Criteria Review**
- **Urine Pregnancy Test** (for all females of childbearing potential) if clinically indicated
- **Pain on Movement (POM) assessment in both the knees- 100mm VAS**
- **WOMAC pain score assessment of the target knee**
- **Study Medication and Subject Diary Dispensing for Run-in Period:** Placebo gel for run-in period will be dispensed by the site staff to qualified subjects. A subject diary, containing instructions for subjects, will be dispensed to each qualified subject. First administration of gel will be supervised at the study center.
- **Instructions on placebo application and storage**
- **First placebo gel application at the site**

- **Assess Adverse Events**
- **Assessment of Concomitant Medications.**

10.3 Treatment Period Visits

10.3.1 Visit 3 (Baseline): Day 0

The following procedures will be performed at the Randomization Visit:

- **Physical Examination and Vital Signs**
- **Inclusion/Exclusion Criteria Review**
- **Urine Pregnancy Test** (for all females of childbearing potential) if clinically indicated.
- **Laboratory investigations** (if not performed within 14 days of baseline visit)
- **Pain on Movement (POM)** assessment in both the knees- 100mm VAS
- **WOMAC pain score assessment of the target knee**
- **Subject diary (placebo run-in period) review and its collection**
- **Assessment of treatment compliance**
- **Application site reaction assessment**
- **Study medication and Subject diary for treatment period dispensing:** Study medication for treatment period will be dispensed by the site staff to qualified subjects. A subject diary, containing instructions for subjects, will be dispensed to each qualified subject.
- **Instructions on study medication application and Storage**
- **Collection of the unused IP dispensing during placebo run-in period**
- **Rescue medication dispensing**
- **Assess Adverse Events**
- **Assessment of Concomitant Medications**

10.3.2 Visit 4: Interim Visit (Week 2/Day 14 ± 4)

The following procedures will be performed.

- **Physical Examination and Vital signs**
- **Urine Pregnancy Test** (for all females of childbearing potential) if clinically indicated.
- **Subject diary review**
- **Assessment of treatment compliance**

- **Pain on Movement (POM) assessment in both the knees- 100mm VAS**
- **WOMAC pain score assessment of the target knee**
- **IMP dispensing**
- **Collection of the unused IPs**
- **Rescue medication dispensing (if required)**
- **Application site reaction assessment**
- **Assess Adverse Events**
- **Assessment of Concomitant Medications.**

10.3.3 Visit 5: End of Study (Week 4/Day 28 ± 4)/Early Termination Visit

The following procedures will be performed.

- **Physical Examination and Vital Signs**
- **Serum Pregnancy Test (for all females of childbearing potential)**
- **Laboratory investigations**
- **ECG**
- **Pain on Movement (POM) assessment in both the knees- 100mm VAS**
- **WOMAC pain score assessment of the target knee**
- **Subject diary (treatment period) review and its collection**
- **Assessment of treatment compliance**
- **Collection of the unused IPs and rescue medication**
- **Application site reaction assessment Collection of unused medications (IP/NIMPs)**
- **Assess Adverse Events**
- **Assessment of Concomitant Medications**

Note:

- ⇒ Additional assessments could be performed as per Investigators' discretion during the study.
- ⇒ All the subjects will be instructed to apply the gel next day (Day 1) onwards.
- ⇒ Telephone contact: Principal investigator or designee will contact the subjects approximately midway between the visit 3-4 and visit 4-5 for assessment of the well-being, adverse event, concomitant medication, and treatment compliance. Additional telephonic contact will be done

to remind the subject regarding stoppage of rescue medication usage prior to scheduled visits (Visit 4, and Visit 5). The same will be documented in the source notes.

⇒ In case subject extends run-in period beyond 11 days, continuation of the subject will be decided in consultation with Medical monitor.

10.4 Unscheduled Visit

An unscheduled visit is allowed at any time if in the investigator's opinion it is warranted. If the investigator assesses the subject's condition at any time and determines that the subject's condition has worsened to the degree that it is unsafe for the subject to continue in the study (including suspected use of placebo), the subject may be discontinued from the study as treatment failure, and a standard of care treatment may be advised at the investigator's discretion.

If subject is discontinued early from the study, Day 28/ Early Termination Visit activities will be performed (see [Appendix II](#)).

11 ADVERSE EVENT REPORTING

11.1 Assessment of Safety

11.1.1 Safety Parameters

Safety may be assessed by the monitoring of adverse clinical events, electrocardiograms, clinical laboratory evaluations and physical examinations. All adverse events occurring during the study must be recorded according to Section '**Adverse Events**'.

11.2 Adverse Events

The adverse event collection period begins at signing of informed consent and continues until 28 days after the last dose. Adverse events occurring during this period need to be reported to the sponsor according to Section '**Documentation of Adverse Events**'.

The investigator is also responsible for notifying the sponsor if he/she becomes aware of any adverse event after the study period has ended and it is considered related to the study medication (i.e. an adverse drug reaction).

Once an AE is detected, it should be followed until its resolution or until it is judged by the principal investigator to be stable or permanent.

11.2.1 Definitions

Adapted from ICH Harmonised Tripartite Guideline: Clinical Safety Data Management Definition and Standards for Expedited Reporting: E2A

Adverse Event:

Any untoward medical occurrence in a patient or clinical trial subject administered a medicinal product and which does not necessarily have to have a causal relationship with this treatment. An AE can therefore be any unfavorable and unintended sign (including a new, clinically important abnormal laboratory finding), symptom, or disease, temporally associated with, whether or not related to the product.

Examples of adverse events include but are not limited to:

- A new disease or exacerbation of an existing disease. Note: worsening of osteoarthritis pain of the knee (disease progression), the condition under study, will not be recorded as an adverse event.
- A recurrence of an intermittent condition (e.g., migraine) not present at baseline;
- A deterioration in a laboratory value or other clinical test (e.g., ECG, X-ray) that is considered clinically significant by the investigator or associated with symptoms or leads to a change in study treatment, concomitant therapy, or discontinuation from study drug;
- A symptom or medical complication related to a protocol-mandated intervention, including screening and run-in period procedures.

Serious Adverse Event:

Any adverse event that:

- Results in death
- Is life-threatening – means an event in which the subject was at risk of death at the time of the event; it does not refer to an event which hypothetically might have caused death if it were more severe
- Requires inpatient hospitalization – any patient admission to a healthcare facility, even if for less than 24 hours. A planned hospitalization required by the protocol or scheduled prior to study initiation does not constitute an SAE
- Prolongs hospitalization – any extension of hospitalization
- Results in persistent or significant disability/incapacity - the term disability means a substantial disruption of a person's ability to conduct normal life functions. This definition is not intended to include experiences of relatively minor medical significance such as uncomplicated headache, nausea, vomiting, diarrhea, influenza, and accidental trauma (e.g. sprained ankle) which may interfere or prevent everyday life functions but do not constitute a substantial disruption
- Is a congenital anomaly/birth defect. A pregnancy during the study meets the seriousness criteria in the following cases: miscarriage, congenital anomaly, neonatal death, infant death

- Is an important medical event that may not be immediately life-threatening or result in death or hospitalization, but may jeopardize the patient or may require intervention to prevent one of the other listed outcomes listed in the definition above? Examples of such events are any cancer, intensive treatment in an emergency room or at home for allergic bronchospasm, blood dyscrasias or convulsions that do not result in hospitalization, or development of drug dependency or drug abuse.

Treatment emergent adverse event:

Any adverse event that occurs after the first dose of study medication through 28 days after the last dose.

Unexpected adverse event/Adverse Drug Reaction:

An expected AE or adverse drug reaction (ADR) is defined as one whose nature or severity is consistent with the reference safety information in the approved label.

An AE is considered unexpected if the nature or severity is not consistent with the applicable product reference safety information. Reports that add significant information on specificity or severity of a known, already documented ADR constitute unexpected events.

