11.2.2 Documentation of Adverse Events

The investigator or designee must record all adverse events reported by subjects that have occurred during the adverse event collection period of the study.

Adverse events should be solicited from subjects through open-ended questions, and as appropriate, by examination. Subjects should normally be evaluated for adverse events following drug administration and prior to discharge from the clinic. The subject should also be queried for any previously unreported adverse event as part of study exit procedures.

All adverse events, whether or not caused by the study drug, will be recorded on source documents and reported to the Sponsor as per [Section 11.2.5](#). The information in the source document will include:

- The date/time of onset of any new adverse event or the worsening of a previously observed adverse event or worsening of any previously existing disease
- The event in standard medical terminology
- The date of resolution of the adverse event, when applicable
- The relationship of the adverse event to the study drug(s)
- The severity of the adverse event

- Seriousness of the adverse event
- Description of action taken in treating the adverse event and/or change in study drug administration or dose

Any abnormal laboratory test results (hematology, clinical chemistry, or urinalysis) or other safety assessments (e.g., ECGs, vital signs measurements), including those that worsen from baseline, and felt to be clinically significant in the medical and scientific judgment of the investigator are to be recorded as AEs or SAEs. The following are examples of laboratory abnormalities that would normally qualify as adverse events:

- The abnormality suggests a change in disease severity and/or organ toxicity
- The abnormality is of a degree that requires active management; e.g. change of dose, discontinuation of the drug, more frequent follow-up assessments, further diagnostic investigation, etc.

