11.2.5 Expedited Reporting of Serious Adverse Events

In addition to standard documentation of adverse events in the source and CRF, serious adverse events require immediate notification to Mylan Product Safety and Risk Management (PSRM). “Immediate” is defined as within 24 hours of the investigator’s or site staff’s knowledge of the event. Serious adverse events are defined in [section 11.2.1 ‘Serious Adverse Events’](#).

The SAE Reporting Form is to be completed for all serious AEs, signed by the investigator, and emailed or faxed with supporting documentation (e.g. case report forms, hospital records, laboratory reports, etc.). Subject identity details (such as but not limited to name or clinic/hospital number) must not be visible on SAE forms or any supporting documentation provided by the Investigator. Any personal information on supporting documents should be redacted before submission to Mylan. **The**

study specific subject ID must be recorded on every page of the SAE report form and supporting documents sent to Mylan.

The investigator will include a narrative description of the serious adverse event(s) that discusses:

- Study medication(s) administered, including dates
- Date and time of the onset of the serious adverse event
- Signs and symptoms
- Description of the event in standard medical terminology
- Date the event resolved or outcome of the event at last observation
- Laboratory and/or confirmatory tests
- Investigator's assessment - the attribution of the adverse event to the study drug(s) or possible alternative etiologies for the event. If considered related (i.e. definite, probable, possible) to the study medication, the rationale for suspecting an adverse drug reaction should be provided
- Description of action taken in treating the adverse event and/or change in study drug administration or dose

The report form must also contain the subject's demographic information, medical history, and concomitant medication at the time of the event.

All communication of AE/SAE information will be in English.

All SAEs must be sent within 24 hours of awareness to:

Mylan [REDACTED]

[REDACTED]
Note: Email is the preferred method of communication

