11.2.5.2 Reporting Timelines for Serious Adverse Events and Follow-up Information

Prompt notification of SAEs by the investigator to Mylan is essential so that legal obligations and ethical responsibilities towards the safety of subjects are met.

Mylan has a legal responsibility to notify both the local regulatory authority and other regulatory authorities about the safety of a product under clinical investigation. Mylan will comply with country specific regulatory requirements relating to safety reporting to the regulatory authority, Institutional Review Board (IRB)/Independent Ethics Committee (IEC) and investigators.

In order for Mylan to meet these obligations, the Principal Investigator (or designee) will report to the Mylan any AE classified as serious via telephone, fax, or email within 24 hours of awareness. All available information must be included on the SAE Report form as soon as possible, but in any case no later than 2 calendar days after first knowledge of the SAE. The notification to the Sponsor should be directed to the safety contact [REDACTED] the Sponsor CRA in parallel. The same timelines apply to reporting of follow-up information.

The Investigator should also be aware of any reporting requirements under his/her responsibility, such as local institutional review boards or ethics committees.

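### Protocol 11.2.1 keeps worsening knee OA pain out of adverse-event recording with no exception for serious cases, so, read literally, an admission or disability from it is not an SAE

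*Protocol*

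**What the plan says.** Protocol 11.2.1 gives "A new disease or exacerbation of an existing disease" as an example of an adverse event. It then adds a note that "worsening of osteoarthritis pain of the knee (disease progression), the condition under study, will not be recorded as an adverse event". The note carries no qualifier about seriousness.

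The same section opens the definition of a serious adverse event with "Any adverse event that" and lists the criteria. Hospitalisation counts as "any patient admission to a healthcare facility, even if for less than 24 hours", apart from planned admissions. Another criterion reads "Results in persistent or significant disability/incapacity".

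Protocol 11.2.5 requires serious adverse events to be notified to the sponsor's safety group within 24 hours. Protocol 11.2.5.2 applies the same limit to "any AE classified as serious via telephone, fax, or email within 24 hours of awareness". Footnote j to the visit schedule in SAP 11.1 likewise ties 24-hour reporting to SAEs.

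Protocol 11.2.2 lists what the source record of an adverse event must contain. One item is the onset of a new event or of "the worsening of a previously observed adverse event or worsening of any previously existing disease". The knee OA exclusion is not repeated there.

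**The concern.** Leaving ordinary fluctuation of the study condition out of AE counts is sensible, because WOMAC pain is the primary endpoint. The difficulty is that the exclusion is unconditional. Expedited reporting exists for individual serious cases, and here the route to it runs through AE status, which the note removes.

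Such a case is foreseeable. Subjects stop their current OA therapy before baseline, must have POM of at least 50 mm and WOMAC pain of at least 9 to be randomised, and one third (404 of 1212) then receive placebo. Protocol 7.7 and 10.4 themselves provide for worsening that makes it unsafe to continue. At stake is whether the sponsor's safety group hears of the few cases that meet a seriousness criterion, and whether all sites treat them alike.

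**Working it through.** No arithmetic applies; the check is to read the provisions in sequence and look for an exception.

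1. **Is the event an AE?** By the general rule in 11.2.1, exacerbation of an existing disease is an AE. The note in the same bullet removes worsening knee OA pain that is disease progression. Result: not an AE.
2. **Can it be an SAE?** The SAE definition starts from an adverse event and adds a criterion. An event removed at step 1 cannot enter, even if the subject is admitted or disabled. Result: not an SAE.
3. **Does the 24-hour duty apply?** In 11.2.5, 11.2.5.2 and SAP footnote j the trigger is an SAE, or an AE classified as serious. Result: no duty.
4. **Does another provision restore it?** Protocol 11.2.7 covers cancer, emergency room visits without admission, overdose, drug interaction, abuse and medication error. It does not mention worsening OA. No exception appears elsewhere in the protocol or SAP.
5. **Where is the event recorded instead?** Under 7.7 and 10.4 it is a reason for withdrawal or a treatment failure, documented in source notes and the case report form. SAP 7.2 tabulates discontinuations by reason and treatment. None of these carries a seriousness assessment, a causality assessment or a notification to the safety group.
6. **Does the timing leave a further gap?** WOMAC and POM end at Visit 5. AE collection under 11.2 runs to 28 days after the last dose. Between the two, AE reporting is the only planned route, and the note closes it for this event.
7. **How does 11.2.2 fit?** A site that relies on its reference to worsening of existing disease could record the same admission that another site, relying on the note in 11.2.1, would leave out.

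**The case against.** Several points against the concern are sound.

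- **The rule for serious cases is inferred.** The protocol nowhere says that serious worsening is to go unreported. That follows from an unqualified exclusion combined with an SAE definition nested within AE. This stands as a caution on wording, but it does not supply the missing exception.
- **The information is not lost altogether.** Individual withdrawals are documented, trigger the early-termination assessments and are tabulated by arm, and rescue use is summarised. This is true, and it narrows the issue to safety reporting.
- **Other events are unaffected.** The note covers only worsening pain as disease progression. A fall, a gastrointestinal bleed or dermatitis remains an AE and can be an SAE.

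A reader might also infer three stronger things that the documents do not support.

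- **That gel-caused knee pain drops out of the safety endpoints.** The words in parentheses confine the note to disease progression, so pain caused by the gel stays under the general AE definition. Application-site reactions are also assessed at each visit after the start of run-in (Protocol 9.4) and analysed by preferred term (SAP 7.12.1.1). Misclassification is possible, but nothing in the plan directs it.
- **That 11.2.1 and 11.2.2 flatly contradict each other.** The item in 11.2.2 describes the contents of an AE record; it does not define what counts as an AE. The more natural reading is that the specific note governs. What remains is a tension that sites could resolve differently.
- **That a number of missed events can be stated.** Assumed rates of 0.1% and 0.5% would give 0.001 × 1212 = 1.2 and 0.005 × 1212 = 6.1 events, but no rate in the documents supports either figure.

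**Conclusion.** The point holds for serious worsening. If the protocol is followed literally, hospital admission or significant disability from worsening knee OA pain falls outside SAE reporting and appears only as a withdrawal or treatment failure. This assumes that the specific note in 11.2.1 prevails over the general wording in 11.2.2, which is the natural reading but not the only one.

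The size cannot be computed. The number of cases is probably small: treatment lasts four weeks, and subjects with Kellgren-Lawrence grade 4 disease or a tense effusion needing aspiration are excluded. A low expected count is not a reason to leave the gap, because expedited reporting is meant for rare individual cases. The equivalence and superiority analyses are not affected.

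**What to change.** Limit the note in Protocol 11.2.1 to worsening that meets no seriousness criterion. For example: *Worsening of knee OA pain as disease progression is not recorded as an AE unless it meets a seriousness criterion in this section; if it does, it is recorded as an AE and reported as an SAE under 11.2.5.* Add the same limit, or a cross-reference to it, at the relevant item in 11.2.2, and carry it into the eCRF guidance.

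Do not add a second exception for worsening suspected to be caused by the gel. Under 11.2.3 a *possible* relationship counts as suspected, so such a clause could move ordinary lack of efficacy into the TEAE tables, most of all in the arm that works least. Gel-caused pain is reportable without it.

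The cost is a short protocol revision, with the sponsor and IEC/IRB approval that 14.6 requires, and a few more AE and SAE records. SAP 7.12.1 already summarises serious TEAEs, so no new analysis is needed.
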